16.0. Additional Effectiveness Analyses for Primary Outcome (Moderators and Mediators)

Moderator (Aim 1b) Statistical Hypotheses: We hypothesize that for patients with more complex conditions (concomitant mood or anxiety disorders; multisite pain) or challenging social / environmental factors (rural/medically underserved or unmet social needs) the contact with a live coach will result in better pain-severity outcomes when compared to those receiving painTRAINER.

Moderator (Aim 1b) Analyses: Subgroup analyses will be conducted to determine the impact of the active interventions on specific populations and explore for potential heterogeneity of treatment effects by sex, age, race/ethnicity, rural/medically underserved residency, multiple pain conditions, mental health mood disorders, and negative social determinants of health. Analyses for Aim 1b will follow the same general approach as for Aim 1 but will be focused on assessing heterogeneity of treatment effects (sub-groups). We will assess heterogeneous treatment effects by each potential moderator separately. For each moderator, we will include in the regression models described in the analytic plan for Aim 1, a main effect for the moderator and an interaction between the moderator, intervention, and follow-up time, to estimate time-specific intervention effects within each subgroup defined by the potential moderator. The primary comparison for Aim 1b will be of the interaction terms associated with each intervention arm at the 3-months follow-up time. The longitudinal nature of data collection will allow us to qualitatively assess if the treatment effectiveness pattern is different over time in each of the intervention groups at the two levels of each of the moderators.

Mediator (Aim1c) Statistical Hypotheses: We hypothesize that changes in pain catastrophizing, pain-related self-efficacy, and perceived support from baseline to 3 months will be mediators of treatment outcomes at 6 months for those in both active interventions.

Mediator (Aim 1c) Analyses: We will use mediation analyses to assess and quantify the effect of theory-based mediators (pain-catastrophizing, pain self-efficacy, perceived support). Mediators represent a causal pathway between the intervention and outcome. Mediation occurs when the intervention influences a variable (the mediator) that in turn subsequently influences the outcome variable. Controlling for a mediator variable causes the strength of relationship between intervention and outcome to be meaningfully reduced. Consistent with recommendations, we will conduct mediation analyses only for interventions that have significant impacts on the outcomes under consideration at 6 months. Primary mediation analyses will assess the effect of the potential mediators on the primary outcome at 6 months, MCID in pain severity, while explanatory secondary analyses will investigate mediator impacts on secondary outcomes at 6 months. We will conduct mediation analyses using the framework recommended by Baron and Kenney²⁴ but using more recent statistical methods developed to better quantify and decompose different aspects of the mediation effect.²⁵ We will run a separate set of mediator analyses for each intervention compared to usual care. We will illustrate our approach for the binary outcome, achieving MCID in pain severity at 6 months.

Our statistical approach for mediation analysis will be to first demonstrate an association between the interventions and the binary outcome, achieving MCID in pain severity at 6 months (step 1; Aim 1).

Step 1 Model:

$$\log(E(Y_i)) = \beta_0 + \beta_1 Int_i + \boldsymbol{\beta}_z \mathbf{Z}_i$$

where Y_i is the binary outcome achieve MCID in pain at 6 months for participant i ($i=1,\dots,n$), Int_i is 1 if the participant i is randomized to given intervention group and 0 otherwise and \mathbf{Z}_i is a vector of baseline adjustment covariates.

We will then demonstrate an association between the interventions and change in each mediator at 3 months (step 2). To do this, we will construct a regression model for each potential mediator under consideration, with the change between the value of the mediator recorded at 3 months and baseline as the dependent variable including a main effect for the intervention. We will do this for each potential mediator and include in the next step only those mediators that are associated with either intervention group with a p-value less than 0.10 (test based on β_{M1} below).

Step 2 Model:

$$E(M_i) = \beta_{Mo} + \beta_{M1} Int_i + \beta_{Mz} Z_i$$

where M_i is the change in mediator of interest from baseline to 3 months for participant i and we will fit this model using linear regression.

The next step (step 3) will be to demonstrate the reduction of the intervention effect on the outcome after removing the effect of the mediator(s). To do this, we will construct a multi-mediator inverse probability weighted (IPW) regression model. This approach allows us to estimate the direct effect of the intervention after rebalancing the intervention and UC groups with respect to the mediators. The application of the IPW approach, as compared to the traditional approach of adjusting for multiple mediators, will allow us to more appropriately account for confounding between a mediator and the outcome both by additional mediators and by other measured variables. Specifically, we will first model the probability of receiving the active intervention given the change in mediators from baseline to 3 months (all mediators that were found associated with intervention in step 2) using logistic regression adjusting for potential baseline confounders (Step 3a).

Step 3a Model:

$$\text{logit}(E(Int_i)) = \beta_{Wo} + \beta_{WM} Msub_i$$

where $Msub_i$ is vector of the subset of mediators that are shown to be associated with the intervention group in Step 2. This model will be used to construct weights defined as the inverse of the estimated probability that each person was assigned to their intervention given their observed mediator value. Specifically, the weights will be:

$$w_i = \begin{cases} \{\exp(\hat{\beta}_{Wo} + \hat{\beta}_{WM} Msub_i)\}/(1 + \exp(\hat{\beta}_{Wo} + \hat{\beta}_{WM} Msub_i))\}^{-1} & \text{for } Int_i = 1 \\ \{1 - \exp(\hat{\beta}_{Wo} + \hat{\beta}_{WM} Msub_i)\}/(1 + \exp(\hat{\beta}_{Wo} + \hat{\beta}_{WM} Msub_i))\}^{-1} & \text{for } Int_i = 0 \end{cases}$$

We will then use these weights to fit a weighted regression model for the binary outcome, achieving MCID in pain severity at 6-months, applying the same mean model as Step 1 except using the weights w_i . In this approach, the weights in essence “weigh out” the effect of the mediator at 3 months. Comparing the estimates of the intervention effect in the weighted and unweighted models will allow us to estimate how much the intervention effect on the outcome can be explained by each potential mediator. We will further be able to quantify the amount of effect explained by each mediator independent of the other mediators.

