15.7 Additional Effectiveness Analyses for Primary Outcome (Moderators and Mediators)

Moderator (Aim 1b) Statistical Hypotheses: For patients with more complex conditions (concomitant mood or anxiety disorders; multisite pain) or challenging social / environmental factors (rural/medically underserved or unmet social needs) the contact with a telephonic coach will result in better pain-severity outcomes when compared to those receiving online CBT-CP.

Moderator Analyses: Subgroup analyses will be conducted to determine the impact of the active interventions on specific populations and explore for potential heterogeneity of treatment effects by sex, age, race/ethnicity, rural/medically underserved residency, multiple pain conditions, mental health mood disorders, and negative social determinants of health. Analyses for Aim 1b will follow the same general approach as for Aim 1 but will be focused on assessing heterogeneity of treatment effects (sub-groups). Heterogeneous treatment effects by each potential moderator will be assessed separately. For each moderator, included in the regression models described in the analytic plan for Aim 1 will be a main effect for the moderator and an interaction between the moderator, intervention, and follow-up time, to estimate time-specific intervention effects within each subgroup defined by the potential moderator. The primary

comparison for Aim 1b will be of the interaction terms associated with each intervention arm at the 3-months follow-up time.

Mediator (Aim1c) Statistical Hypotheses: Changes in pain catastrophizing, pain-related self-efficacy, and perceived support from baseline to 3 months will be mediators of treatment outcomes at 6 months for those in both active interventions.

Mediator Analyses: Mediation analyses will be used to assess and quantify the effect of theory-based mediators (pain-catastrophizing, pain self-efficacy, perceived support). Primary mediation analyses will assess the effect of the potential mediators on the primary outcome at 6 months, MCID in pain severity, while explanatory secondary analyses will investigate mediator impacts on secondary outcomes at 6 months.

The RESOLVE SAP provides further detail on the planned moderator and mediator analyses.

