14.0. Primary Effectiveness Analyses

Primary Outcome Statistical Hypothesis: Both active interventions (painTRAINER and virtual coach-led CBT-CP) are expected to result in a higher proportion of patients achieving MCID (30% reduction in overall BPI-SF score) in pain severity relative to those receiving usual care at 3-month follow-up (primary time point).

Secondary Time Point Statistical Hypotheses: Both active interventions (painTRAINER and virtual coach-led CBT-CP) are expected to result in a higher proportion of patients achieving MCID (30% reduction in overall BPI-SF score) in pain severity relative to those receiving usual care at the 6 and 12-month follow-ups (secondary time points).

Primary Outcome and Secondary Time Point Analyses: We will use modified Poisson regression^{20,21} fit using generalized estimating equations (GEE) to model the binary primary outcome, MCID in pain severity (30% reduction from baseline), 3 months (primary time point) and 6 and 12 months (secondary time points). We are employing modified Poisson (i.e., Poisson family with log link, but use robust standard errors to correct for mis-specified outcome variance) instead of logistic regression since the binary outcome is not rare and the estimate of interest is the relative risk. We will use a working independence correlation matrix and will calculate standard errors using the robust sandwich estimator to account for within-person and within-health coach correlation^{21,22} and account for the mis-specified mean-variance structure when using Poisson regression for a binary outcome.^{20,23} We will include interactions between each intervention and indicators of time (3, 6, 12 months) to estimate time-specific intervention effects; the primary comparisons will be between the interventions and usual care at 3 months (i.e., primary effectiveness will test the size of the intervention coefficient at the 3-months timepoint). We will adjust for baseline levels of pain severity, other stratification variables (sex, clinical site, and rural/medically underserved residency), and a priori variables predictive of outcome (multisite pain and co-occurring mental health condition). Specifically, we will fit the following mean model where Usual Care and 3 months are the reference groups:

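### The primary comparison named for Aim 1b is not the coach-versus-painTRAINER contrast that the aim's hypothesis is about

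*SAP*

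**What the plan says.** The Aim 1b hypothesis is head-to-head. For patients with mood or anxiety disorders, multisite pain, rural or underserved residence, or unmet social needs, SAP 16.0 expects that "the contact with a live coach will result in better pain-severity outcomes when compared to those receiving painTRAINER". Protocol 15.7 has the same hypothesis: "the contact with a telephonic coach will result in better pain-severity outcomes when compared to those receiving online CBT-CP".

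The analysis is described differently. SAP 16.0 states that "Analyses for Aim 1b will follow the same general approach as for Aim 1", adds the moderator and its interaction with arm and time to the Aim 1 model "to estimate time-specific intervention effects within each subgroup defined by the potential moderator", and then sets the test: "The primary comparison for Aim 1b will be of the interaction terms associated with each intervention arm at the 3-months follow-up time". Protocol 15.7 names the same terms.

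The Aim 1 model is in SAP 14.0: "we will fit the following mean model where Usual Care and 3 months are the reference groups". Its main tests are also against usual care: "the primary comparisons will be between the interventions and usual care at 3 months". Subgroup power in SAP 5.0 and Protocol 15.1 is given only for each intervention against usual care.

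**The concern.** In a model coded against usual care, an arm-by-moderator interaction is the change in that arm's effect versus usual care from one moderator level to the other. The hypothesis concerns the difference between the two active arms among complex patients. These are different quantities and can point in opposite directions. If both programs work better in complex patients, both named terms can be significant with no coach advantage. If the coach is better than painTRAINER to the same degree in everyone, both named terms are null although the hypothesis is true.

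At stake is the interpretation of Aim 1b. The pre-specified result could support or contradict its only stated hypothesis for a reason unrelated to that hypothesis, and the choice of contrast that answers it would be left until the data are in hand. Aim 1 is not affected.

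**Working it through.** **Notation.** At 3 months, on the log risk-ratio scale: b1 and b2 are the painTRAINER and coach effects versus usual care when the moderator is absent; g1 and g2 are their moderator interactions.

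- Terms named as primary, natural reading: g1 and g2.
- Literal hypothesis, coach better than painTRAINER among complex patients: (b2 − b1) + (g2 − g1) > 0.
- Whether the coach advantage differs by moderator level: g2 − g1.

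**The plan's own figures (SAP 5.0).** Inputs: 621 evaluable per arm, usual care 15%, intervention 22.5%, 90% power, omnibus test followed by pairwise tests at 0.05. Simulating that two-step rule with the third arm at 15% gives 90.7% power at 621 per arm, and 621/0.80 = 776.25, rounded up to 777 per arm or 2,331 in all. For the subgroup table (stated power 80%) the same simulation gives 82.4%, 82.2% and 81.9% at N = 372, 558 and 744. The figures reproduce closely, and all are for an intervention against usual care.

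**Two constructed cases.** The documents give no planned coach-versus-painTRAINER difference, so the rates are assumed. Per arm: 744/3 = 248 complex and 621 − 248 = 373 non-complex. Variance of a log proportion: (1 − p)/(np). Two-sided 0.05.

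*Case A: usual care/painTRAINER/coach = 15/20/30% at both levels.* Here g1 = g2 = 0, so each named term rejects at 5%. Coach versus painTRAINER in complex patients: ln(0.30/0.20) = 0.405; SE = √[0.80/(248×0.20) + 0.70/(248×0.30)] = 0.160; z = 2.54; power = Φ(2.54 − 1.96) = 72% (73% by simulation). The interaction g2 − g1 is also zero and rejects 5%.

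*Case B: 15/15/15% in non-complex, 15/30/30% in complex.* Here g1 = g2 = ln 2 = 0.693; SE = √[2×0.85/(373×0.15) + 0.85/(248×0.15) + 0.70/(248×0.30)] = 0.250; z = 2.77; power = Φ(2.77 − 1.96) = 79% for each named term (80% by simulation). The coach/painTRAINER risk ratio in complex patients is exactly 1, and its test rejects 5%.

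**Less extreme cases.** 200,000 simulated trials each; 621 per arm, usual care 15% throughout, active arms averaging 22.5%, moderator prevalence 40-50%. For g1 and g2 the basis is always at least one significant.

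| Truth | g1 or g2 significant | g2 − g1 significant |
|---|---|---|
| Coach/painTRAINER ratio of risk ratios 1.82, split evenly around usual care | 44-46% | 79-81% |
| Both arms gain equally in complex patients (ratio 1.49 each) | 50-51% | 5% |

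In the first row each named term alone has 22-23% power. With a 2-df omnibus step in the manner of SAP 10.0, the 50-51% falls to 33-34% and the 79-81% falls to 68-71%.

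The within-complex contrast does not win everywhere. In the first row at 50% prevalence, √1.82 = 1.349, so the lower and higher rates are 0.225/[(1 + 1.349)/2] = 19.2% and 19.2% × 1.349 = 25.8%. Among complex patients painTRAINER is at 19.2% and coach at 25.8%, with about 311 per arm: log ratio 0.299, SE 0.151, z = 1.98, power about 51%.

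**Power for the head-to-head contrast within the complex level** (two proportions, two-sided 0.05, painTRAINER assumed at 15-25%):

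| Subgroup N (per arm) | Difference detectable with 80% power |
|---|---|
| 372 (124) | 14.8 to 16.7 points |
| 558 (186) | 11.8 to 13.5 points |
| 744 (248) | 10.0 to 11.6 points |

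With painTRAINER at 22.5%, power for a 5-point coach advantage is 15%, 20% and 25% at the three sizes; for 7.5 points it is 27%, 38% and 48%. Coach clustering and covariate adjustment are not modelled.

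**The case against.** Four points can be made for the plan.

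1. *The sentence does not name usual care.* A comparison of the two arms' interaction terms could mean g1 against g2, which is a coach-versus-painTRAINER moderation test, and the hypothesis just before it is head-to-head. This stands as a possible reading. It is not the natural one given the reference coding, the Aim 1 tests and the power table, and even this reading misses the literal hypothesis in Case A.

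2. *SAP 10.0 extends a similar three-group approach to secondary analyses, and SAP 5.0 places Aim 1b among them.* A pairwise coach-versus-painTRAINER test is therefore arguably allowed. That stands too, but being allowed is not being named as primary, and SAP 16.0 names something else. A reader might infer that the trial cannot test its hypothesis, or that the head-to-head contrast could only be an unplanned extra. The documents do not support either: the contrast is a linear combination of coefficients in the planned model.

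3. *Aim 1b is wider than its hypothesis.* It also covers sex, age and race/ethnicity, for which no head-to-head hypothesis is stated and arm-by-moderator terms are suitable. This is a good reason to keep those terms, but not to make them the test of the stated hypothesis.

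4. *The simulated figures depend on assumed rates.* True. The ratio of 1.82 with opposite shifts is favourable to g2 − g1, and an omnibus step lowers the numbers. The mismatch between contrast and hypothesis does not depend on them.

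**Conclusion.** The point holds as a mismatch between hypothesis and named test. On the natural reading, the primary Aim 1b terms can be null when the coach is truly better (Case A: 5% rejection each, against 72-73% for the within-complex contrast) and significant when the two programs are equal (Case B: about 79% each, against 5%). Neither document writes out a coach-versus-painTRAINER contrast for Aim 1b or states its power.

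Two stronger statements should be avoided. The named terms do not compare each arm with usual care; they compare each arm's effect versus usual care across moderator levels. Nor is g2 − g1 alone the right replacement: it rejects only 5% of the time in Case A, where the literal hypothesis is true.

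The percentages rest on assumed rates and are illustrative; the algebra is not. For a secondary aim this should be corrected before unblinding.

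**What to change.** In SAP 16.0 and Protocol 15.7, for the four hypothesised moderators (mood or anxiety disorder, multisite pain, rural or underserved residence, unmet social needs):

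- Name as the primary Aim 1b comparison the 3-month coach-versus-painTRAINER risk ratio within the complex level, (b2 − b1) + (g2 − g1).
- Report with it the coach-minus-painTRAINER interaction, g2 − g1, as the test of whether that advantage differs by moderator level.
- Keep the versus-usual-care interactions as the descriptive heterogeneity analysis for all moderators, including sex, age and race/ethnicity.
- Say whether the SAP 10.0 omnibus step applies to these contrasts.
- Add to SAP 5.0 and Protocol 15.1 the head-to-head detectable differences, with the painTRAINER rate stated as an assumption and an allowance for coach clustering.

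The cost is a few sentences in each document and two contrast statements on the model already planned, with no new data. The drawback is that the plan will have to show openly that head-to-head power within subgroups is modest.

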Pain catastrophizing	Pain Catastrophizing Scale (PCS)– Short Form 6 ¹⁵ (6-item; continuous)	Patient self-report at baseline and 3 months
Pain self-efficacy	Self-Efficacy for Pain Management subscale of the Chronic Pain Self-Efficacy Scale ¹⁶ (5-item; continuous)	Patient self-report at baseline and 3 months
Perceived support	2 items; developed in UG3 phase	Patient self-report at notification of randomization and 3 months

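### The displayed mediation weights use change scores and no mediator baseline, so the mediated share is understated if the 6-month outcome depends on the mediator's 3-month level

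*SAP*

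**What the plan says.** In SAP 16.0, Step 2 regresses the mediator on arm and covariates, "where M_i is the change in mediator of interest from baseline to 3 months for participant i". Step 3 will "model the probability of receiving the active intervention given the change in mediators from baseline to 3 months". In the displayed Step 3a equation the only regressor is Msub, "where $Msub_i$ is vector of the subset of mediators that are shown to be associated with the intervention group in Step 2", and the weight formula repeats that linear predictor. The weights are described as the "inverse of the estimated probability that each person was assigned to their intervention given their observed mediator value". The weighted outcome model is the Step 1 model (arm plus Z). The SAP says informally that the weighting takes out "the effect of the mediator at 3 months".

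Two statements bear on covariates:

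- The sentence introducing Step 3a says the model is fitted "using logistic regression adjusting for potential baseline confounders (Step 3a"). It names no confounders, and the equation has no term for them.
- Z in Steps 1 and 2 is a vector of baseline covariates that Section 16 does not itemise. The only itemised list is for the primary analysis in SAP 14.0: "We will adjust for baseline levels of pain severity, other stratification variables (sex, clinical site, and rural/medically underserved residency), and a priori variables", which are multisite pain and a co-occurring mental health condition. It contains no mediator baseline.

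SAP 4.0 shows that catastrophizing and self-efficacy are both collected by "Patient self-report at baseline and 3 months". Perceived support is first measured when participants are told their assignment. Protocol 15.7 leaves the detail of the mediation analysis to the SAP.

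**The concern.** A change score contains the baseline value with a negative sign: people who start high tend to fall more. Randomization balances the mediator's baseline across arms. Forcing the arms to have the same distribution of change undoes that balance. Since the 3-month level is baseline plus change, the level stays different between arms as well. The weights then do not remove the mediator at 3 months, which is how the SAP describes their purpose.

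Aim 1c is meant to quantify how much of the 6-month effect passes through the theory-based mediators. If the 6-month outcome responds to the mediator's level at 3 months, the leftover difference appears as a direct effect and the mediators look weaker than they are. A larger sample does not cure this.

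**Working it through.** The documents give no figure for the mediation analysis, so there is none to reproduce.

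**Inputs from the documents.** The Step 1, 2 and 3a models and the weights are from SAP 16.0. The rates are 15% under usual care and 22.5% under intervention (RR 1.5), with 621 evaluable per arm, from SAP 5.0. SAP 5.0 states these rates for 3 months; they are assumed here for 6 months. The self-efficacy effect size of 0.43 is from Protocol 4.5.

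**Assumed inputs, not in the documents.** Baseline-to-3-month correlation ρ of 0.4–0.8; intervention shift a of 0.3–0.6 SD; ratio k of 3-month SD to baseline SD of 0.8–1.2; mediator–baseline-pain correlation of 0.4 unless stated. The whole effect passes through the mediator.

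**Step 1: algebra.** Let M0 be the baseline value with SD 1, M3 the 3-month value with within-arm SD k, and D = M3 − M0. The intervention shifts M3 by a.

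- Within arm, Cov(M0, D) = ρk − 1 and Var(D) = 1 + k² − 2ρk.
- At a given D, the arms differ in M0 by a × (1 − ρk)/(1 + k² − 2ρk). Weighting on D equalises D, so this difference remains in M0 and therefore in M3.
- Equal SDs (k = 1): (1 − ρ)/(2 − 2ρ) = 0.5 for every ρ. With a = 0.40, M0 and M3 each stay 0.20 SD apart; with a = 0.43, 0.215 SD.
- k = 0.8, ρ = 0.6: 0.52/0.68 = 0.76 of the shift remains.
- k = 1.2, ρ = 0.6: 0.28/1.00 = 0.28 remains. Away from k = 1 the fraction also depends on ρ.

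**Step 2: simulation of the displayed steps.** This used 300,000 or more per arm, logistic weights, and a weighted Poisson outcome model with arm and baseline pain. Reported share = 1 − log(weighted RR)/log(unweighted RR). With equal SDs and a level-driven outcome the RR falls only from 1.50 to about 1.20, and 1 − 0.182/0.405 = 0.55.

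| What drives the 6-month outcome | Displayed weights | M0 added to Step 3a |
|---|---|---|
| 3-month level, equal SDs | 52–57% | 97–101% |
| Level, k = 0.8 (ρ = 0.6) | about 29% | about 99–101% |
| Level, k = 1.2 (ρ = 0.6) | about 75% | about 99–101% |
| Level minus half of baseline | 74–78% | 98–101% |
| Change alone | 93–99% | 99–101% |

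The correct answer in every row is 100%.

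**Step 3: variations on the level-driven, equal-SD case.**

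- Baseline pain added to the weights: about 55–59%. This is the Section 14 covariate most relevant here, and it does not repair the problem.
- Mediator–baseline-pain correlation raised to 0.6: 61–66%.
- M0 added to the outcome model only, with weights still on change alone: about 79% at ρ = 0.6 (69–89% for ρ of 0.4–0.8).
- 621 per arm, 1,000 simulated trials: median 54% (10th–90th percentile 38–85%) with the displayed weights, and median 98% (73–146%) with M0 in Step 3a.

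**The case against.** **The Step 3a text promises confounder adjustment.** This stands in part. A reader might infer that the plan never allows for the mediator's baseline. The documents do not support that: the text mentions baseline confounders, and Section 16 does not say that Z equals the Section 14 list. If the unnamed set includes the mediator's baseline, the bias disappears. But nothing says that it does, and the equation and weight formula carry no such term. An analyst who follows the formulas, or who adds the itemised covariates, gets the bias.

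**The hypothesis is about change.** SAP 16.0 and Protocol 15.7 both hypothesise that changes in the mediators carry the effect, and the phrase about removing the mediator at 3 months is informal. This also stands in part: if change alone is the mechanism, the displayed weights lose almost nothing. But the documents do not establish that mechanism, and the corrected model performs as well or better under every mechanism tested.

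**The size depends on the model.** This stands. In a further fully mediated model, the mediator drives pain equally strongly at baseline and follow-up. There the displayed weights report 76–91%, or 84–95% with baseline pain added. The shortfall remains but is well short of half.

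**The consequence is limited.** Mediation is run only for interventions with a significant 6-month effect, no effectiveness result changes, and the error understates mediation rather than inventing it. A single trial's mediated share is imprecise in any case. All of this is true, but imprecision does not excuse a systematic shortfall that can be removed with data already collected.

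**Conclusion.** The concern holds in a conditional form. As displayed, Step 3a balances change and unbalances the mediator's baseline, by half of the arm's effect on the mediator when the two SDs are equal. The mediated share is understated whenever the 6-month outcome depends on the 3-month level. With a fully level-driven outcome and the assumed values above, the report is about 52–57% of a fully mediated effect with equal SDs, and about 29–75% for SD ratios of 0.8 to 1.2.

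A reader might infer that the trial will report half of any mediated effect. The documents do not support that. They give no SDs, retest correlations or mechanism for the mediators, the loss is smaller under mixed mechanisms, and it is almost nil if change alone acts. What is firm is that the text and equation of Step 3a disagree, that no mediator baseline is named, and that both the displayed formula and the itemised covariates leave the bias in place. The SAP should be changed; the primary and secondary effectiveness analyses are unaffected.

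**What to change.** For catastrophizing and self-efficacy, add the pre-randomization value M0 in SAP 16.0 as follows:

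- **Step 2:** include M0 as a covariate.
- **Step 3a:** write the model as logit P(Int) on Msub, M0 and Z, and put the same terms in the weight formula, so that the equation matches the text. Itemise Z.
- **Outcome models:** include M0 in both the unweighted and weighted models, so that the two are comparable. Adding it here alone is not enough.

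With M0 in Step 3a, change and 3-month level give the same weights, so the change-score definition can stay.

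State that this does not extend cleanly to perceived support. Its first measurement is mailed with the notification of assignment (Protocol 11.2), so it comes after randomization and is not a clean pre-treatment covariate.

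The cost is one already-collected covariate per mediator and a few more parameters in the weight model. No new data are needed.
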